11.4.8.3.4 Lung diffusion capacity

Descriptive summary statistics for observed treatment-emergent values and changes from core baseline (expressed in absolute change and % of predicted value) in DL_{CO} by visit will be provided by core study treatment for the Combined Analysis Period using the SAF.

11.4.8.3.5 Pulmonary safety events

Treatment-emergent pulmonary safety events over the Combined Analysis Period for subjects who received ponesimod 20 mg in the core study only, will be summarized in a similar manner to AEs and will include the events:

- Pulmonary AEs or SAEs of special interest;
- Withdrawal due to pulmonary reasons/AE.

The analysis of other pulmonary variables will be described in the SAP.

^{**} applies only to subjects who have no exposure to commercially available ponesimod prior to the EOS visit.

^{**} applies only to subjects who have no exposure to commercially available ponesimod prior to the EOS visit.

EudraCT 2016-004719-10 EDMS-ERI-207656619

Confidential

11.4.8.4 Vital signs

15 March 2022, page 143/216

Descriptive summary statistics by visit will be provided for observed treatment-emergent values and absolute change from core baseline for HR, sBP, dBP and body weight by core study treatment for the Combined Analysis Period using the SAF. These parameters will also be summarized descriptively for the Extension Analysis Period by core study treatment, and overall using the EXTS.

Treatment-emergent notable BP abnormalities will also be summarized for both analysis periods. The definition for notable abnormalities is provided in Appendix 5.

11.4.8.5 Laboratory endpoints

Descriptive summary statistics by visit will be provided for observed treatment-emergent values and absolute change from core baseline for laboratory tests (hematology, blood chemistry, urinalysis) by core study treatment for the Combined Analysis Period using the SAF. These parameters will also be summarized descriptively for the Extension Analysis Period by core study treatment and overall using the EXTS.

Treatment-emergent laboratory notable abnormalities will be summarized for subjects who received ponesimod 20 mg in the core study only for the Combined Analysis Period using the SAF.

The definition for notable abnormalities is provided in Appendix 5 and include:

- Treatment-emergent laboratory test abnormalities based on normal ranges of the central laboratory, project-specific ranges, and common terminology criteria for adverse events (CTCAE) [CTCAE 2010; see Appendix 5]
- Treatment-emergent laboratory test abnormalities based on FDA guidance for DILI [FDA 2009b] (for ALT / AST / total bilirubin).

Lymphocyte count reversibility after EOT will be summarized descriptively by comparing the mean (and 95% CIs) for absolute change in lymphocyte counts from core baseline to EOS, and from core baseline to EOT.** This analysis will be performed for the Combined Analysis Period by core study treatment using the SAF.

** applies only to subjects who have no exposure to commercially available ponesimod prior to the EOS visit.

11.4.8.6 eC-SSRS

The number and percentage of subjects with a treatment-emergent eC-SSRS suicidal ideation score of 4 or above, or a "yes" response on the eC-SSRS suicidal behavior item will be summarized descriptively by core study treatment for the Combined Analysis Period.

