Other endpoints		
 Absolute values and change from baseline for HR, SBP, DBP and body weight at all assessments 	Y	Y
• Treatment-emergent notable blood pressure abnormalities##	Y	Y
 Absolute values and change from baseline for laboratory tests (hematology, blood chemistry, urinalysis) at all assessments 	Y	Y
• Treatment-emergent notable laboratory abnormalities##	Y	Y
 Change from baseline to EOS versus change from baseline to EOT in lymphocyte counts (absolute and percent change)** 	Y	N
• Treatment-emergent eC-SSRS suicidal ideation score of 4 or above, or a "yes" response on the eC-SSRS suicidal behavior item	Y	N

Cumulative safety data, i.e., AEs for the combined analysis period will only be presented for subjects who received 20 mg ponesimod in the core study.

The selection of AEs of special interest [see Appendix 4] is based on the anticipated risks of treatment with ponesimod; the final list of AEs of special interest will be defined in the SAP.

The selection of notable abnormalities considered for the analyses is based on standard definitions and the anticipated risks of treatment with ponesimod; the final list of abnormalities will be defined in the SAP.

^{**} Only for subjects who have no exposure to commercially available ponesimod prior to the EOS visit.

AE = adverse event; DBP = diastolic blood pressure; DL_{CO} = diffusing capacity for the lungs measured using carbon monoxide; eC-SSRS = electronic self-rated version of the Columbia-Suicide Severity Rating Scale; ECG = electrocardiogram; EOS = End-of-Study; EOT = End-of-Treatment; FEV_1 = forced expiratory volume in 1 second; FVC = forced vital capacity; HR = heart rate; QTcB = QT corrected for heart rate on the basis of Bazett's formula; QTcF = QT corrected for heart rate on the basis of Fridericia's formula; SAE = serious adverse event; SAP = statistical analysis plan; SBP = systolic blood pressure.

15 March 2022, page 89/216

Confidential

EudraCT 2016-004719-10 EDMS-ERI-207656619

The treatment-emergent period is defined as the time from first ponesimod administration in the applicable Analysis Period up to 15 days (inclusive) after last study treatment administration. This definition applies regardless of whether the subject receives commercially available ponesimod after completing study treatment.

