11.1.4.2 Combined analysis period

For efficacy this period includes all available data from randomization in the core study up to the extension EOS date for subjects entering the extension, or up to the core EOS date for subjects not entering the extension. For safety this period includes all available data from the date of first treatment administration up to the last treatment date + 15 days in the extension study for subjects entering the extension, or up to the last treatment date + 15 days in the core study for subjects not entering the extension.

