11.2.3 Safety Set

The Safety Set (SAF) includes all subjects who received at least one administration of core study treatment. Subjects will be analyzed according to the treatment they received during the core study.

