11.4.8 Analysis of the safety variables

If not otherwise stated, only safety data considered treatment-emergent (up to 15 days after the last treatment administration) in the respective analysis period [as defined in Section 11.1.4] will be included in tables and figures. All safety data will be included in listings, with flags for safety data not considered to be treatment-emergent to a specific analysis period.

Generally, safety data is presented as follows:

Safety data collected in the extension study will be analyzed based on the **Extension Analysis Period** using the EXTS and will be summarized for all subjects overall and split by core study treatment group. The analysis of change from baseline for safety endpoints assessed by visit will use the extension baseline as reference.

Furthermore, the long-term safety of ponesimod 20 mg and the changes in safety for teriflunomide 14 mg subjects switching to ponesimod 20 mg will be assessed by summarizing all data in the **Combined Analysis Period** using the SAF. Cumulative data such as AEs and SAEs will only be summarized for subjects initially treated with ponesimod 20 mg in the core study. Safety endpoints assessed by visit will be summarized by core study treatment group. Analysis of change from baseline for safety endpoints assessed by visit will use the core baseline as reference.

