11.4.8.3.1 Absolute values and change from baseline

Descriptive summary statistics by visit for the Combined Analysis Period using the SAF will be provided for observed (absolute and percent of predicted) treatment-emergent values and changes from core baseline for FEV₁, FVC and FEV₁/FVC ratio (all expressed in absolute change, % change).

The mean (and 95% CIs) for change from core baseline to EOS and from core baseline to EOT for FEV_1 and FVC (absolute change, percent change and absolute change in % predicted)** will be plotted by core study treatment for the Combined Analysis Period using the SAF.

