11.4.8.3.3 Reversibility of treatment-emergent decreases in FEV₁ and FVC

For the subset of subjects with a decrease of ≥200 mL or ≥12% in FEV1 or FVC from core baseline at EOT, the number and percentage of subjects with a decrease of <200 mL and <12% from core baseline to EOS** in FEV1 or FVC will be summarized for subjects who received ponesimod 20 mg in the core study only for the Combined Analysis Period using the SAF.

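### The lymphocyte reversibility analysis and the FEV₁/FVC plot to EOT and EOS pool teriflunomide stoppers with ponesimod stoppers in the core-teriflunomide row

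*Protocol*

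**What the plan says.** Section 11.4.8.5 states: "Lymphocyte count reversibility after EOT will be summarized descriptively by comparing the mean (and 95% CIs) for absolute change in lymphocyte counts". Both changes start at core baseline; one ends at the EOS visit, the other at the EOT visit. The section then fixes set, period and grouping: "This analysis will be performed for the Combined Analysis Period by core study treatment using the SAF". Section 11.4.8.3.1 treats FEV₁ and FVC alike: mean changes from core baseline to EOS and to EOT "will be plotted by core study treatment for the Combined Analysis Period using the SAF".

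The definitions behind these sentences are:

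- Section 11.2.3: "The Safety Set (SAF) includes all subjects who received at least one administration of core study treatment". Subjects are analysed by the treatment received in the core study.
- Section 11.1.4.2: the combined safety period runs to 15 days after the last extension dose for entrants, "or up to the last treatment date + 15 days in the core study for subjects not entering the extension".
- Section 3.1: all entrants receive ponesimod 20 mg, whatever their core arm.
- Table 9 (Section 6.2): the EOS-versus-EOT endpoints are marked Yes for the Combined Analysis Period and No for the Extension Analysis Period, with the footnote "Only for subjects who have no exposure to commercially available ponesimod prior to the EOS visit".

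The analysis that the protocol itself titles FEV₁/FVC reversibility (Section 11.4.8.3.3) is set up differently. It "will be summarized for subjects who received ponesimod 20 mg in the core study only for the Combined Analysis Period using the SAF".

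**The concern.** An EOT-to-EOS contrast describes what happens when a drug is stopped, so it can be read only if everyone in a row stops the same drug. Grouping by core arm on the SAF does not ensure this for the core-teriflunomide arm. Non-entrants stop teriflunomide at the end of the core study, while entrants stop ponesimod at the end of the extension.

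Recovery of the lymphocyte count and of lung function after ponesimod are listed safety endpoints. A reader comparing the two core-arm rows would take a difference as an effect of exposure history, when part of it may come from the mix of drugs. Because the contrasts are not planned for the Extension Period, no other planned table separates the two groups.

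**Working it through.** **Step 1: who stops what.** The protocol gives no figure for these analyses to reproduce, so the composition of the rows is derived from its definitions.

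| Core arm | Entered extension? | Last EOT/EOS | Drug stopped |
|---|---|---|---|
| Ponesimod | Yes | Extension | Ponesimod |
| Ponesimod | No | Core | Ponesimod |
| Teriflunomide | Yes | Extension | Ponesimod |
| Teriflunomide | No | Core | Teriflunomide |

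The core-ponesimod row mixes exposure durations but not drugs. The core-teriflunomide row mixes drugs.

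**Step 2: planned composition.** Section 11.6 gives 1100 core subjects and about 800 entrants, and Section 5.1.7 puts about half of core subjects on teriflunomide. Equal entry by arm is assumed, as is that every non-entrant has both an EOT and an EOS value.

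- Core-teriflunomide arm: 1100 / 2 = 550; entrants 800 / 2 = 400; non-entrants 550 − 400 = 150.
- Teriflunomide-stopper share: 150 / 550 = 27%.
- Unequal entry: if 40% of entrants came from teriflunomide, there are 320 entrants and 230 non-entrants, a share of 230 / 550 = 42%. If 60%, 480 and 70, a share of 70 / 550 = 13%.
- Missing values: if only half of the 150 non-entrants had both values, the share is 75 / (75 + 400) = 16%.

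**Step 3: the commercial-ponesimod exclusion.** The core study was completed in May 2019 (Section 1.3.2), and the October 2020 entry in the amendment summary still treats commercial availability as a future event. The exclusion can therefore remove only extension entrants. With a fraction f of entrants removed (assumed; the protocol gives no rate), the share is 150 / (150 + 400(1 − f)).

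**Step 4: illustration for lymphocytes.** Section 1.3.2.2 gives a mean reduction of 65.3% on 20 mg at Week 24 of the Phase 2 study. The protocol gives no teriflunomide effect, so 0% to −20% is assumed. With s the share from Step 3 and t the teriflunomide change, the row's change at EOT is s × t + (1 − s) × (−65.3%).

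| f (assumed) | Teriflunomide-stopper share | Row change, t = 0% | t = −10% | t = −20% |
|---|---|---|---|---|
| 0 | 150/550 = 27% | −47.5% | −50.2% | −52.9% |
| 0.25 | 150/450 = 33% | −43.5% | −46.9% | −50.2% |
| 0.50 | 150/350 = 43% | −37.3% | −41.6% | −45.9% |
| 0.75 | 150/250 = 60% | −26.1% | −32.1% | −38.1% |

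If the row held extension entrants only, the same input would give −65.3% at every f. The calculation uses percentages, whereas Section 11.4.8.5 specifies absolute change in counts, so it shows direction and rough size only. The protocol has no input for a matching FEV₁/FVC calculation.

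**The case against.** The strongest reply is that the safety sections never say that core EOT and EOS values of non-entrants enter these analyses. Used without qualification, EOT and EOS are normally the extension visits (Sections 3.2.3.1 and 3.2.4), and core visits are usually labelled as such. Section 11.3.1.3 adds core EOS for non-entrants explicitly, for disability accumulation. If only extension visits are meant, non-entrants contribute nothing and the row holds ponesimod stoppers alone.

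That reading is possible, but it fits poorly with a set that includes non-entrants and a combined safety period that ends in the core study for them. If it was intended, the SAF is the wrong set and the EXTS should be named. The text needs changing on either reading.

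Other parts of the reply stand:

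- The by-visit laboratory summaries on the EXTS (Section 11.4.8.5) show the on-ponesimod lymphocyte effect in switchers unmixed. They do not supply the EOS contrast.
- Non-entrants include early core discontinuers, some of whom may lack an EOT or EOS value, so 27% is an upper figure under equal entry and no exclusion.
- A reader might infer that the EOS visit, 30 to 44 days after stopping (Section 8.4.1), is lost because the safety period ends at 15 days. Section 11.4.8 applies that limit only if nothing else is stated, and these analyses name EOS as their timepoint, which largely answers the point.

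**Conclusion.** The point holds for two analyses: lymphocyte reversibility in Section 11.4.8.5 and the FEV₁/FVC plot in Section 11.4.8.3.1. As written, their core-teriflunomide row pools two drugs and cannot be read as reversibility after ponesimod. The mixing follows from the definitions, provided that EOT and EOS for non-entrants are their core visits. Its size, up to about 27% before the commercial-ponesimod exclusion and more after it, rests on planned numbers, equal arms and entry, and complete values. The dilution of the lymphocyte change rests further on assumed commercial uptake and an assumed teriflunomide effect.

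Three stronger readings are not supported:

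- That FEV₁/FVC reversibility as a whole is compromised. Section 11.4.8.3.3 is limited to core-ponesimod subjects.
- That the row says nothing about ponesimod. Before any exclusion, 400 / 550 = 73% of it are ponesimod stoppers on planned numbers.
- That the core-ponesimod row is mostly subjects with at most 108 weeks of exposure. On the same planned split this needs 400(1 − f) < 150, that is, more than 62.5% of entrants excluded, and no such rate is given.

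The study is descriptive with no pre-specified hypotheses (Section 11.4.1), so no error rate is affected.

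**What to change.** In Sections 11.4.8.5 and 11.4.8.3.1, group the EOT-versus-EOS analyses by the drug last taken:

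- Restrict the core-teriflunomide row to extension entrants (EXTS), at extension EOT and EOS.
- Show core-teriflunomide non-entrants at core EOT and EOS as a separate teriflunomide row, or omit them.
- State which study's EOT and EOS are used for entrants and for non-entrants.

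This takes a sentence or two in each section and no new data. The cost is smaller rows and at most one extra row: on planned numbers about 400 switchers before the commercial-ponesimod exclusion, and up to about 150 teriflunomide stoppers shown apart.

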11.4.8.7 Other Safety Variables

The analysis of all other safety variables will be described in detail in the SAP.

Confidential

EudraCT 2016-004719-10 EDMS-ERI-207656619

11.4.9 Immunogenicity Analysis

15 March 2022, page 144/216

The following humoral immune responses are measured, based on the COVID-19 immunogenicity samples, including S- and N-ELISA assays and titers of neutralizing antibodies in a subset of samples.

- SARS-CoV-2 binding antibodies to S protein (ELISA): Analysis of antibodies binding to SARS-CoV-2 S protein
- SARS-CoV-2 seroconversion based on antibodies to N protein (ELISA): Analysis of antibodies binding to SARS-CoV-2 N protein
- SARS-CoV-2 neutralization (wtVNA): Analysis of neutralizing antibodies to the wild-type virus

Descriptive statistics of assays will be presented overall, by vaccination type, and by COVID-19 AE status as applicable.

11.5 Interim analyses

An unblinded interim analysis will be performed after the randomization list unblinding of the core study. Further interim analyses may be performed subsequent to this date.

11.5.1 Additional periodic analyses

During the conduct of the study, data analyses might be performed at specified intervals of time (eg, all patients who complete 12 months of treatment).

11.6 Sample size

As the extension study is an extension of the confirmatory Phase 3 core study, there are no sample size statistical considerations. The sample size will be pragmatically determined by how many of the 1100 subjects planned in the core phase enroll into the extension study. Based on anticipated discontinuation rates in the core study, approximately 800 subjects are expected to enter the extension study.

12 DATA HANDLING

12.1 Data collection

The investigator/delegate is responsible for ensuring the accuracy, completeness, and timeliness of the data reported. All source documents should be completed in a neat, legible manner to ensure accurate interpretation of the data. Data reported in the eCRF derived from source documents must be consistent with the source documents.

eCRF data will be captured via electronic data capture (EDC; using the Rave system provided by Medidata Solutions, Inc., a web-based tool). The investigator and site staff will be trained to enter and edit the data via a secure network, with secure access features (username, password, and identification – an electronic password system). A complete electronic audit trail will be maintained. The investigator/delegate will approve the data (i.e., confirm the accuracy of the data recorded) using an electronic signature (ref. to 21 CFR Part 11).

15 March 2022, page 145/216

Confidential

EudraCT 2016-004719-10 EDMS-ERI-207656619

Subject pre-treatment and treatment data will be completed for all subjects (i.e., eligible and non-eligible) through the eCRF.

For each subject enrolled (i.e., from whom an informed consent has been obtained), regardless of study treatment initiation, an eCRF must be completed and signed by the investigator/delegate. This also applies to those subjects who fail to complete the study. If a subject withdraws from the study, the reason must be noted on the eCRF.

12.2 Maintenance of data confidentiality

The investigator/delegate must ensure that data confidentiality is maintained. On eCRFs or other documents (e.g., documents attached to SAE reports) submitted to the sponsor and any external service providers, subjects must be identified only by number, and never by name or initials, hospital numbers, or any other identifier. The investigator/delegate must keep a subject identification code list, at the site, showing the enrollment number, the subject's name, date of birth, and address or any other locally accepted identifiers. Documents identifying the subjects (e.g., signed informed consent forms) must not be sent to the sponsor, and must be kept in strict confidence by the investigator/delegate.

12.3 Database management and quality control

Electronic CRFs will be used for all subjects. The investigator will have access to the site eCRF data until the database is locked. Thereafter, they will have read-only access. The eCRF must be kept current to reflect subject status at any timepoint during the course of the study.

While entering the data, the investigator/delegate will be instantly alerted to data queries by validated programmed checks. Additional data review will be performed by the sponsor on an ongoing basis to look for unexpected patterns in data and study monitoring. If discrepant data are detected, a query specifying the problem and requesting clarification will be issued and visible to the investigator/delegate via the eCRF. All electronic queries visible in the system either require a data correction (when applicable) and a response from the investigator/delegate to clarify the queried data directly in the eCRF, or simply a data correction in the eCRF. The investigator/delegate must, on request, supply the sponsor with any required background data from the study documentation or clinical records. This is particularly important when errors in data transcription are suspected. In the case of health authority queries, it is also necessary to have access to the complete study records, provided that subject confidentiality is protected.

This process will continue until database closure.

Laboratory samples, ECGs, SF-36v2TM,eC-SSRS assessments will be processed through a central laboratory/provider and the results will be sent electronically to the sponsor. Any data received from central laboratory or central ECG facility generated in relation to follow up on adverse events which are ongoing at end of study should be entered in the database even if obtained after the EOS visit.

15 March 2022, page 146/216

Confidential

EudraCT 2016-004719-10 EDMS-ERI-207656619

After the database has been declared complete and accurate, the database will be closed. Any changes to the database after that time may only be made as described in the appropriate SOP. After database closure, the investigator will receive the eCRFs of the subjects of her/his site (including all data changes made) on electronic media or as a paper copy.

13 PROCEDURES AND GOOD CLINICAL PRACTICE

13.1 Ethics and Good Clinical Practice

The sponsor and the investigators will ensure that the study is conducted in full compliance with ICH-GCP Guidelines, the principles of the "Declaration of Helsinki", and with the laws and regulations of the country in which the research is conducted.

